12.4 Response Criteria for Patients with Solid Tumor and Measurable Disease

12.4.1 Evaluation of Target Lesions

Complete Response (CR): Disappearance of all target and non-target lesions. Any pathological lymph nodes (whether target or non-target) must have reduction in short axis to <10 mm. If immunocytology is available, no disease must be detected by that methodology. Normalization of urinary catecholamines or other tumor markers if elevated at study enrollment (for patients with neuroblastoma).

Partial Response (PR):	At least a 30% decrease in the sum of the diameters of target lesions, taking as reference the baseline sum diameters
Progressive Disease (PD):	At least a 20% increase in the sum of the diameters of target lesions, taking as reference the smallest sum on study (this includes the baseline sum if that is the smallest on study). In addition to the relative increase of 20%, the sum must also demonstrate an absolute increase of at least 5 mm. (Note: the appearance of one or more new lesions is also considered progressions). Note: in presence of SD or PR in target disease but unequivocal progression in non-target or non-measurable disease, the patient has PD if there is an overall level of substantial worsening in non-target disease such that the overall tumor burden has increased sufficiently to merit discontinuation of therapy
Stable Disease (SD):	Neither sufficient shrinkage to qualify for PR nor sufficient increase to qualify for PD, taking as reference the smallest sum diameters while on study

12.4.2 Evaluation of Non-Target Lesions

Complete Response (CR):	Disappearance of all non-target lesions and normalization of tumor marker level. All lymph nodes must be non-pathological in size (<10 mm short axis) Note: If tumor markers are initially above the upper normal limit, they must normalize for a patient to be considered in complete clinical response.
Non-CR/Non-PD:	Persistence of one or more non-target lesion(s) and/or maintenance of tumor marker level above the normal limits
Progressive Disease (PD):	Appearance of one or more new lesions and/or unequivocal progression of existing non-target lesions. Unequivocal progression should not normally trump target lesion status. It must be representative of overall disease status change, not a single lesion increase.

12.4.3 **Overall Response Assessment**

Table 1: For Patients with Measurable Disease (i.e., Target Disease)

Target Lesions	Non-Target Lesions	New Lesions	Overall Response	Best Overall Response when Confirmation is Required*
CR	CR	No	CR	≥ 28 days Confirmation
CR	Non-CR/Non-PD	No	PR	≥ 28 days Confirmation
CR	Not evaluated	No	PR	
PR	Non-CR/Non-PD/not evaluated	No	PR	
SD	Non-CR/Non-PD/not evaluated	No	SD	documented at least once ≥ 28 days from baseline
PD	Any	Yes or No	PD	no prior SD, PR or CR
Any	PD**	Yes or No	PD	
Any	Any	Yes	PD	

* See RECIST 1.1 manuscript for further details on what is evidence of a new lesion.
** In exceptional circumstances, unequivocal progression in non-target lesions may be accepted as disease progression.

Note: Patients with a global deterioration of health status requiring discontinuation of treatment without objective evidence of disease progression at that time should be reported as "symptomatic deterioration." Every effort should be made to document the objective progression even after discontinuation of treatment.

Table 2: For Patients with Non-Measurable Disease (i.e., Non-Target Disease)

Non-Target Lesions	New Lesions	Overall Response
CR	No	CR
Non-CR/non-PD	No	Non-CR/non-PD*
Not all evaluated	No	not evaluated
Unequivocal PD	Yes or No	PD
Any	Yes	PD

* 'Non-CR/non-PD' is preferred over 'stable disease' for non-target disease since SD is increasingly used as an endpoint for assessment of efficacy in some trials so to assign this category when no lesions can be measured is not advised

Table 3: Overall Response for Patients with Neuroblastoma and Measurable Disease

CT/MRI	MIBG	Bone Scan	Bone Marrow	Catechol	Overall
PD	Any	Any	Any	Any	PD
Any	PD	Any	Any	Any	PD
Any	Any	PD	Any	Any	PD
Any	Any	Any	PD	Any	PD
SD	CR/PR/SD	Non-PD	Non-PD	Any	SD
PR	CR/PR	Non-PD	Non-PD	Any	PR
CR/PR	PR	Non-PD	Non-PD	Any	PR
CR	CR	Non-PD	Non-PD	Elevated	PR
CR	CR	CR	CR	Normal	CR

12.4.4 Overall Best Response Assessment

Each patient will be classified according to his "best response" for the purposes of analysis of treatment effect. Best response is determined as outlined in [Section 12.9](#) from a sequence of overall response assessments.

12.5 **Response Criteria for Neuroblastoma Patients with MIBG Positive Lesions**12.5.1 MIBG Positive Lesions

Patients who have a positive MIBG scan at the start of therapy will be evaluable for MIBG response. The use of ^{123}I for MIBG imaging is recommended for all scans. If the patient has only one MIBG positive lesion and that lesion was radiated, a biopsy must be done at least 28 days after radiation was completed and must show viable neuroblastoma.

12.5.2 The following criteria will be used to report MIBG response by the treating institution:

Complete response: Complete resolution of all MIBG positive lesions

Partial Response: Resolution of at least one MIBG positive lesion, with persistence of other MIBG positive lesions

Stable disease: No change in MIBG scan in number of positive lesions

Progressive disease: Development of new MIBG positive lesions

[figure not shown]
12.5.3 The response of MIBG lesions will be assessed on central review using the Curie scale¹⁴ as outlined below. Central review responses will be used to assess efficacy for study endpoint. See [Section 8.2](#) for details on transferring images to the Imaging Research Center.

NOTE: This scoring should also be done by the treating institution for end of course response assessments.

The body is divided into 9 anatomic sectors for osteomedullary lesions, with a 10th general sector allocated for any extra-osseous lesion visible on MIBG scan. In each region, the lesions are scored as follows. The **absolute extension score** is graded as:

- 0 = no site per segment,
- 1 = 1 site per segment,
- 2 = more than one site per segment,
- 3 = massive involvement (>50% of the segment).

The **absolute score** is obtained by adding the score of all the segments. See diagram of sectors below:

The **relative score** is calculated by dividing the absolute score at each time point by the corresponding pre-treatment absolute score. The relative score of each patient is calculated at each response assessment compared to baseline and classified as below:

1. **Complete response:** all areas of uptake on MIBG scan completely resolved. If morphological evidence of tumor cells in bone marrow biopsy or aspiration is present at enrollment, no tumor cells can be detected by routine morphology on two subsequent bilateral bone marrow aspirates and biopsies done at least 21 days apart to be considered a **Complete Response**.
2. **Partial response:** Relative score ≤ 0.2 (lesions almost disappeared) to ≤ 0.5 (lesions strongly reduced).
3. **Stable disease:** Relative score > 0.5 (lesions weakly but significantly reduced) to 1.0 (lesions not reduced).
4. **Progressive disease:** New lesions on MIBG scan.

12.5.4 Overall Response Assessment

Table 4: Overall Response Evaluation for Neuroblastoma Patients and MIBG Positive Disease Only

If patients are enrolled without disease measurable by CT/MRI, any new or newly identified lesion by CT/MRI that occurs during therapy would be considered progressive disease.

MIBG	CT/MRI	Bone Scan	Bone Marrow	Catechol	Overall
PD	Any	Any	Any	Any	PD
Any	New Lesion	Any	Any	Any	PD
Any	Any	PD	Any	Any	PD
Any	Any	Any	PD	Any	PD
SD	No New Lesion	Non-PD	Non-PD	Any	SD
PR	No New Lesion	Non-PD	Non-PD	Any	PR
CR	No New Lesion	Non-PD	Non-PD	Elevated	PR
CR	No New Lesion	CR	CR	Normal	CR

12.5.5 Overall Best Response Assessment

Each patient will be classified according to his “best response” for the purposes of analysis of treatment effect. Best response is determined from the sequence of the overall response assessments as described in [Section 12.9](#).

12.6 **Response Criteria for Neuroblastoma Patients with Bone Marrow Involvement**

12.6.1 Bone Marrow Involvement

Note: patients with bone marrow as the ONLY site of disease are not eligible for this study. Response criteria in this section are intended to be used when assessing marrow involvement as a component of overall response.

Histologic analysis at the local institution of marrow tumor cell involvement is **required** for patients with a history of marrow involvement. Marrow aspirate and biopsy should be evaluated at baseline and every 2 cycles thereafter. Note: If progressive disease is documented by RECIST criteria using tumor measurements or by MIBG scan, then a repeat BM is not needed to confirm PD.

Complete Response: No tumor cells detectable by routine morphology on 2 consecutive bilateral bone marrow aspirates and biopsies performed at least 21 days apart. Normalization of urinary catecholamines or other tumor markers if elevated at study enrollment.

Progressive Disease: In patients who enroll with neuroblastoma in bone marrow by morphology have progressive disease if there is a doubling in the amount of tumor in the marrow AND a minimum of 25% tumor in bone marrow by morphology. (For example, a patient entering with 5% tumor in marrow by morphology must increase to $\geq 25\%$ tumor to have progressive disease; a patient entering with 30% tumor must increase to $> 60\%$).

In patients who enroll without evidence of neuroblastoma in bone marrow will be defined as progressive disease if tumor is detected in 2 consecutive bone marrow biopsies or aspirations done at least 21 days apart.

Stable Disease: Persistence of tumor in bone marrow that does not meet the criteria for either complete response or progressive disease.

12.6.2 Overall Best Response Assessment

Each patient will be classified according to his “best response” for the purposes of analysis of treatment effect. Best response is determined from the sequence of the overall response assessments as described in [Section 12.9](#).

12.7 **Response Criteria for Patients with CNS Tumors**

12.7.1 Measurable Disease

Any lesion that is at minimum 10 mm in one dimension on standard MRI or CT, for CNS tumors.

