4.1 Inclusion Criteria

4.1.1 APEC1621SC: Patient must have enrolled onto APEC1621SC and must have been given a treatment assignment to MATCH to APEC1621G based on the

presence of a BRAF V600 mutation (see [Appendix VII](#)).

4.1.2 **Age:** Patients must be \geq than 12 months and \leq 21 years of age at the time of study enrollment.

4.1.3 **BSA:**

4.1.3.1 Patients must have a body surface area $\geq 0.55 \text{ m}^2$ at enrollment. Patients $< 0.73 \text{ m}^2$ must follow the dosing nomogram provided in [Appendix IV-A](#); patients $\geq 0.73 \text{ m}^2$ at enrollment must follow the dosing nomogram provided in [Appendix IV-B](#).

4.1.4 **Disease Status:** Patients must have radiographically **measurable** disease (See [section 12](#)) at the time of study enrollment. Patients with neuroblastoma who do not have measurable disease but have MIBG+ evaluable disease are eligible. Measurable disease in patients with CNS involvement is defined as tumor that is measurable in two perpendicular diameters on MRI and visible on more than one slice.

Note: The following do not qualify as measurable disease:

- malignant fluid collections (e.g., ascites, pleural effusions)
- bone marrow infiltration except that detected by MIBG scan for neuroblastoma
- lesions only detected by nuclear medicine studies (e.g., bone, gallium or PET scans) except as noted for neuroblastoma
- elevated tumor markers in plasma or CSF
- previously radiated lesions that have not demonstrated clear progression post radiation
- leptomeningeal lesions that do not meet the measurement requirements for RECIST 1.1.

4.1.5 **Performance Level:** Karnofsky $\geq 50\%$ for patients > 16 years of age and Lansky ≥ 50 for patients ≤ 16 years of age (See [Appendix I](#)). **Note:** Neurologic deficits in patients with CNS tumors must have been stable for at least 7 days prior to study enrollment. Patients who are unable to walk because of paralysis, but who are up in a wheelchair, will be considered ambulatory for the purpose of assessing the performance score.

4.1.6 **Prior Therapy**

4.1.6.1 Patients must have fully recovered from the acute toxic effects of all prior anti-cancer therapy and must meet the following minimum duration from prior anti-cancer directed therapy prior to enrollment. If after the required timeframe, the numerical eligibility criteria are met, e.g. blood count criteria, the patient is considered to have recovered adequately.

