12.7.3 Selection of Target and Non-Target Lesions

For most CNS tumors, only one lesion/mass is present and therefore is considered a "target" for measurement/follow up to assess for tumor progression/response. If multiple measurable lesions are present, up to 5 should be selected as "target" lesions. Target lesions should be selected on the basis of size and suitability for accurate repeated measurements. All other lesions will be followed as non-target lesions. The lower size limit of the target lesion(s) should be at least twice the thickness of the slices showing the tumor to decrease the partial volume effect (e.g., 8 mm lesion for a 4 mm slice).

Any change in size of non-target lesions should be noted, though does not need to be measured.

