12.7.4 Response Criteria for Target Lesions

Response criteria are assessed based on the product of the longest diameter and its longest perpendicular diameter. Development of new disease or progression in any established lesions is considered progressive disease, regardless of response in other lesions – e.g., when multiple lesions show opposite responses, the progressive disease takes precedence. Response Criteria for target lesions:

- **Complete Response (CR):** Disappearance of all target lesions. Off all steroids with stable or improving neurologic examination.
- **Partial response (PR):** $\geq 50\%$ decrease in the sum of the products of the two perpendicular diameters of all target lesions (up to 5), taking as reference the initial baseline measurements, on a stable or decreasing dose of steroids with a stable or improving neurologic examination.
- **Stable Disease (SD):** Neither sufficient decrease in the sum of the products of the two perpendicular diameters of all target lesions to qualify for PR, nor sufficient increase in a single target lesion to qualify for PD; on a stable or decreasing dose of steroids with a stable or improving neurologic examination.
- **Progressive Disease (PD):** 25% or more increase in the sum of the products of the perpendicular diameters of the target lesions, taking as reference the smallest sum of the products observed since the start of treatment, or the appearance of one or more new lesions.

Increasing doses of corticosteroids required to maintain stable neurological status should be strongly considered as a sign of clinical progression unless in the context of recent wean or transient neurologic change due e.g. to radiation

effects.

12.7.5 Response Criteria for Non-Target Lesions:

- **Complete Response (CR):** Disappearance of all non-target lesions.
- **Incomplete Response/Stable Disease (IR/SD):** The persistence of one or more non-target lesions.
- **Progressive Disease (PD):** The appearance of one or more new lesions and/or unequivocal progression of existing non-target lesions.

12.7.6 Response criteria for tumor markers (if available):

Tumor markers will be classified simply as being at normal levels or at abnormally high levels.

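### CNS measurable disease is one-dimensional in 12.7.1 but two-dimensional in 4.1.4 and 12.7.4, which leaves thin target lesions open to false progression

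*Combined protocol and SAP*

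**What the plan says.** - **Entry, 4.1.4.** Measurable CNS disease is "defined as tumor that is measurable in two perpendicular diameters on MRI and visible on more than one slice". No size in millimetres is given, and the same criterion sends the reader to Section 12.
- **Measurability, 12.7.1.** The definition is "Any lesion that is at minimum 10 mm in one dimension on standard MRI or CT, for CNS tumors". Nothing is asked of the second diameter, and CT is accepted. Section 12.7.2 follows the same logic: disease counts as merely evaluable only when no lesion can be measured in even one dimension.
- **Target selection, 12.7.3.** Up to five targets are taken from the measurable lesions, chosen for size and for how reliably they can be re-measured. The lower size limit is twice the slice thickness ("e.g., 8 mm lesion for a 4 mm slice"). The diameter it applies to is not stated.
- **Response, 12.7.4.** "Response criteria are assessed based on the product of the longest diameter and its longest perpendicular diameter". PR is a fall of at least 50% from baseline in the summed products. PD is "25% or more increase in the sum of the products of the perpendicular diameters of the target lesions", measured from the smallest sum. The same section also treats progression of any one existing lesion as PD whatever the others do, and its SD definition refers to growth in a single target lesion.
- **Absolute floor.** For other solid tumors, 12.4.1 adds that "the sum must also demonstrate an absolute increase of at least 5 mm". Section 12.7.4 has no counterpart.
- **Downstream.** A counted response needs two determinations (12.9) and central review (11.5, 12.3.1.1). A local progression call is a PFS event even if central review disagrees (11.7). Progression ends protocol therapy (10.1). Progression at or before the second evaluation makes the best response PD (12.9, Table 5).

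**The concern.** A product of two diameters is only as reliable as the less reliable diameter. Section 12.7.1 admits a lesion on its long axis alone, so the short axis can be a few millimetres. Because the thresholds are relative, a millimetre of reading error on a short axis moves the product by a large percentage.

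Section 4.1.4 guarantees at least one bidimensional tumor at entry. It does not say how large that tumor must be, and it does not govern which further lesions become targets. Two situations are therefore exposed: a sole target that meets 4.1.4 but is thin, and thin additional targets accepted through 12.7.1. At stake are PFS events, early removal from therapy, and the loss of a genuine response when a false progression comes early.

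**Working it through.** **1. The design the responses feed.** Section 11.3 gives N = 20, success at 3 or more responses, 5% against 25%, alpha 10% and power 90%. Exact binomial: P(X ≥ 3 | 20, 0.25) = 0.909 and P(X ≥ 3 | 20, 0.05) = 0.0755. The stated power is reproduced, and alpha is within its 10% ceiling. The design is not in dispute.

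**2. Change needed in one lesion, long axis held at 10 mm.** With short axis b, the product is 10b. PD needs b to rise by 0.25b; PR needs it to fall by 0.50b.

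| Lesion (mm) | Rise reaching PD | Fall reaching PR | 1 mm more on both axes |
|---|---|---|---|
| 10 x 4 | 1.0 mm | 2.0 mm | 11 x 5 / 40 = +37.5% |
| 10 x 8 | 2.0 mm | 4.0 mm | 11 x 9 / 80 = +23.75% |
| 10 x 10 | 2.5 mm | 5.0 mm | 11 x 11 / 100 = +21% |

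Check: 10 x 5 / (10 x 4) − 1 = +25%, and 10 x 2 / (10 x 4) − 1 = −50%.

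**3. The same thin lesion as an additional target.** Beside a 10 x 10 mm lesion, the baseline sum is 100 + 40 = 140.
- Short axis 4 to 5 mm: 150/140 − 1 = +7%, not PD on the sum.
- Short axis 4 to 2 mm: 120/140 − 1 = −14%, not PR.

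The dilution is firm for PR, which is defined on the sum. For PD it depends on which wording in 12.7.4 governs. On the any-lesion wording, the thin lesion alone has risen 25%.

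**4. The slice-thickness limit.** If it covers both diameters, a 4 mm short axis passes only with slices of 4/2 = 2 mm or less. If it covers the longest diameter only, a 10 x 4 mm lesion passes with slices up to 10/2 = 5 mm.

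**5. Error rates with no true change.** The documents give no measurement error. This simulation (one million draws, one target lesion) *assumes* independent normal error on each diameter, at baseline and at each follow-up, over a range of SDs.

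| Error SD | Lesion (mm) | PR, one scan | PR, two scans | PD, one scan |
|---|---|---|---|---|
| 0.5 mm | 10 x 4 | 0.03% | <0.01% | 12% |
| 0.5 mm | 10 x 10 | <0.01% | <0.01% | 1.3% |
| 1 mm | 10 x 4 | 4.6% | 0.5% | 28% |
| 1 mm | 10 x 10 | 0.04% | <0.01% | 13% |
| 2 mm | 10 x 4 | 20.6% | 6.5% | 39% |
| 2 mm | 10 x 10 | 5.1% | 0.8% | 29% |

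Central review is not modelled.

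**6. What false PR could do to alpha.** Suppose every one of the 20 patients carried an extra false-response probability f. The null rate becomes 0.05 + 0.95f. For f = 0.5%, 1% and 2%, exact alpha is 9.3%, 11.3% and 15.6%. This overstates the effect at any given f, because only CNS patients with thin sole targets are exposed.

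**The case against.** The other side has substantial points.

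- **The entry rule.** Section 4.0 says eligibility is applied literally and cannot be waived. Section 12.7.3 notes that most CNS tumors have a single mass, so the usual target is the lesion that met 4.1.4. This stands, and it narrows the exposure. It does not remove it, because 4.1.4 sets no minimum size.
- **The safeguards in 12.7.3.** A lesion reliable on one axis only is hard to call suitable for repeated bidimensional measurement, and at 4 mm slices a 4 mm axis fails an 8 mm limit. This stands in part: the first condition is a judgment, and the second does not name the diameter.
- **The 8 mm example.** A reader might infer that 12.7.3 admits a target which 12.7.1 calls non-measurable. The text does not establish that. The two conditions can be cumulative, with 10 mm governing at 4 mm slices and 12 mm at 6 mm slices. The example is unclear rather than a proven conflict.
- **False responses in the primary endpoint.** A reader might also infer that thin lesions inflate the response rate. A counted PR needs two determinations at least three weeks apart, central review, stable or falling steroids and a stable or improving neurologic examination. Under the assumed 1 mm SD, two-scan false PR is about 0.5% for a sole thin target, before central review. Even if all 20 patients carried it, alpha would stay below 10%. At a 2 mm SD the figure is 6.5%, but that error is half the short axis, and central review still has to agree.

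Progression has no equivalent protection, so these points do not answer the false-PD concern.

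**Conclusion.** The contradiction is real. Section 12.7.1 is one-dimensional and accepts CT, 4.1.4 is two-dimensional and names MRI only, and 12.7.4 scores a product. The measurability rule does not fit the metric it supplies.

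The consequence is mainly false PD. For a sole 10 x 4 mm target, or for any single lesion on the any-lesion wording, 1 mm on the short axis is enough, against 2.5 mm for a 10 x 10 mm lesion. On the sum it is diluted to +7% in the example above. A false PD can end therapy, count as a PFS event on a local call and, if early, erase a response. With success set at 3 of 20, each lost response matters, but the effect on the primary endpoint is indirect.

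The single-lesion percentages rest on an assumed measurement error. The size at trial level cannot be set, because neither that error nor the CNS share is given. Section 12.7 will nonetheless be used: CNS tumors are in the primary aim, and Appendix VI lists high-grade glioma, ependymoma and medulloblastoma as expansion histologies. This should be corrected. It does not undermine the design.

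**What to change.** Reconcile 4.1.4, 12.7.1, 12.7.2 and 12.7.3 into a single CNS target-lesion definition that states:
- two perpendicular diameters, visible on more than one slice;
- one minimum size in millimetres, applied to both diameters;
- the imaging modality, the same at entry and at follow-up;
- that the twice-slice-thickness limit applies to both diameters, with an example that agrees with the minimum size.

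Follow every other CNS lesion as non-target.

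The cost is a wording change. The small downside is that some thin lesions become non-target. N, alpha and power stay as they are. The change reduces false PD but does not remove it: under the assumed 1 mm SD, a 10 x 10 mm lesion still crosses the 25% threshold on about 13% of single scans, against 28% for a 10 x 4 mm lesion. It also leaves untouched the lack of an absolute floor for CNS progression and the two readings of PD in 12.7.4.
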